Title: Pilot RCT to Evaluate the Effects of a Trust-Building Depression Management Intervention on Moderate Depressive Symptoms in Low-Income Adolescents

NCT: 03599141

Date IRB approved: 10/13/2022

PROTOCOL TITLE: Study comparing two depression management interventions for teens with depression

PRINCIPAL INVESTIGATOR:

[name], RN
Frances Payne Bolton School of Nursing
[contact]
[contact]

UH FACULTY ADVISOR: N/A

OTHER DEPARTMENTS INVOLVED IN THIS STUDY: Department of Psychology

VERSION NUMBER: 1.16

DATE: 09/28/2022

Study Comparing Two Depression Management Interventions for Teens with Depression

Objectives

(1) Our purpose is to test the Trust-building depression Self-Management Together (**TRUST**) intervention among adolescents with moderate depressive symptoms. Our premise is that trust can be learned, that increasing trust will improve self-regulation, and improved self-regulation will influence depression management behaviors, which will decrease depressive symptoms and increase quality of life (QOL). **The study aims are:**

Aim 1. Compare the effects of the TRUST intervention with a depression management intervention on depression management behaviors (sleep, stress management, medication adherence, appointment keeping) and health status (depressive symptoms, QOL) in adolescents with moderate depressive symptoms.

Aim 2. Assess whether the effects of the TRUST intervention on depression management behaviors (sleep, stress management, medication adherence, appointment keeping) and health status (depressive symptoms, QOL) are mediated by (respiratory sinus arrhythmia [RSA], behavioral interaction assessment, adolescent/parent trust self-reports, relationship quality, self-regulation, family cohesion, social support, decision making, self-efficacy, rumination, decentering).

Aim 3. Assess the effects of potential moderators (gender, race, perceived stress, parental monitoring, household income, parent level of education, parenting style, parent stress) on the relationship between the TRUST intervention and depression management behaviors and health status (depressive symptoms, QOL).

(2) **Hypothesis:** We hypothesize that variations in adolescent/ parent trust-building will predict response to the TRUST intervention and depression management behaviors as evidenced by change in depressive symptoms and QOL.

Background

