(1) Depressive symptoms are a serious concern affecting the social, academic, and health outcomes of 36% of Cleveland adolescents.² Health disparities exist in depression management—with low-income and minority adolescents more likely to forego treatment for depression.³ Students enrolled in Cleveland Metropolitan School District (CMSD) schools are 100% low-income and 84% ethnic minority.⁶ We are collaborating with CMSD to address health disparities in depression management among low income and minority adolescents. Our team has an 8-year ongoing relationship with CMSD schools to improve the health of Cleveland's children and their families.

Depression among adolescents is affected by health behaviors such as sleep, stress management, medication adherence, and appointment keeping, as well as quality of relationship with parents. Family focused interventions are well established for reducing emotional and behavioral problems in adolescents, and function in part, by fostering positive adolescent-parent relationships.⁷ Rotenberg describes adolescents' trust of their parent as made up of: (a) honesty, which is telling the truth and engaging in benign and genuine behaviors; (b) reliability, which is perceived compatibility between one's words and actions; and (c) emotional connection, which is the dependence on others to be receptive to disclosures and maintain confidentiality of disclosures.⁸ We are applying this theory as a basis for the TRUST intervention used in this study that builds trust between adolescents and their parents, alongside depression management behaviors.

(2) **Preliminary data.** In this pilot RCT, we are evaluating the effects of the novel TRUST intervention to improve depression management behaviors in adolescents with depressive symptoms. PI [name] has shown that low interpersonal trust is associated with risky health behaviors⁵ and high depressive symptoms in low income adolescents.⁴ Recent studies indicate

that self-regulation is a core aspect of positive relationships,⁹ trust,¹⁰ and healthy behaviors.¹¹ RSA is an indicator of heart rate variability in response to respiration,¹² which is a marker of self-regulation.^{11,13} We will assess RSA during a behavioral assessment of the quality of adolescent-parent interaction using microsocial coding approaches.^{14,15} Co-I [name] has shown that RSA is associated with mutual positive affect¹⁶ and emotion regulation¹⁵ in adolescent-parent behavioral interactions.

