b. **Questionnaires:** Survey data will be collected using REDCap on a tablet computer. Measures used in the study are listed in the Table below. Due to restrictions associated with the COVID-19 pandemic, parents and adolescents will be asked to answer questions privately and at approximately the same time point on an electronic device connected to the internet in their homes. If, for example, only one electronic device is able to connect to the internet, the adolescent can complete the survey and then pass the device to the parent for survey completion. We are assessing families for internet access and device availability in the screening form. For families that do not have a device, we will mail them a tablet that they will mail back to us at the end of the study.

Study Variables, Measures, and Data Collection Points						
ADOLESCENT SURVEY						
Variable	Instrument	Title on Survey	B	3M	6M	
Depressive symptoms	Patient Health Questionnaire-8 ¹⁹	Depression Questions	X	X	X	
Quality of life	Youth Quality of Life-Short Form ²¹	Quality of Life Questions	X	X	X	
Sleep	PROMIS sleep disturbance-4 ²⁵ Children's Report of Sleep Patterns ²²	Sleep Questions More Sleep Questions	X X	X X	X X	
Stress management	Adolescent Lifestyle Questionnaire—stress management subscale ²³	How do you handle your stress?	X	X	X	
Medication adherence	Extent of Medication Adherence ²⁴	Medication Questions	X	X	X	
Appointment keeping	Hill-Bone Compliance Scale ²⁵	Appointment Questions	X	X	X	
Biologic Trust	Respiratory sinus arrhythmia ¹³	Not applicable—assessment in lab	X	X		
Behavioral Trust	Behavioral interaction assessment ¹⁴	Not applicable—assessment in lab	X	X		
Cognitive Trust	Children's General Trust Scale ²⁶	Children's Trust Questions	X	X	X	
Cognitive Trust	Parent Trust of Child Scale—Adolescent perceived ²⁷	Parental Trust Questions	X	X	X	
Relationship quality	Inclusion of Other in Self ²⁸	How close are you with your parent?	X	X	X	
Self-regulation	Positive and Negative Affect Schedule ²⁹	Emotion Questions	X	X	X	

Family cohesion	Brief Family Relationship Scale ³⁰	Family Relationship Questions	X	X	X
Rumination	Children's Response Style Questionnaire ³²	How do you handle sadness?	X	X	X
Self-efficacy	PROMIS Self-efficacy - Youth ³¹	Getting stuff done questions	X	X	X
Decentering	Experiences Questionnaire ³³	Self-awareness Questions	X	X	X
Demographics	Demographics questionnaire	Who are you?	X		
Perceived stress	Perceived Stress Scale-Peds ³⁴	Stress Questions	X	X	X

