	Group 1	Group 2
Prescreening	5 minutes	5 minutes
Screening	30 minutes	30 minutes
Study Visit 1 (Baseline)	30 minutes	30 minutes
Intervention week 1	45 minutes	1 hours
Intervention week 2	45 minutes	1 hours
Intervention week 3	45 minutes	1 hours
Intervention week 4	45 minutes	1 hours
Intervention week 5	45 minutes	1 hours
Intervention week 6	45 minutes	1 hours
Intervention week 7	45 minutes	1 hours
Intervention week 8	45 minutes	1 hours
Study Visit 2 (3 months)	30 minutes	30 minutes
Study Visit 3 (6 months)	30 minutes	30 minutes
Total	8 hours 5 minutes	10 hours 35 minutes

ClinicalTrials.gov Information

Has this study been registered on ClinicalTrials.gov?

Yes. Provide the following:

- i. The ClinicalTrials.gov identifier: 00220503
- ii. Investigator/sponsor responsible for registering: [name]

No. Explain if there are plans to register or why registration is not required.

List of Data to be Collected

1. Indicate what identifiers you will collect

- Name
- Address
- Dates related to an individual (*birthdate*)
- Telephone number
- Fax number
- Email address

- Social security number
- Medical record number
- Health plan beneficiary number
- Account number
- Certificate/license number
- Any vehicle or other device serial
- Device identifiers or serial numbers
- Web URL
- Internet protocol (IP) address
- Finger or voice prints
- Photographic (video) images
- Other: Any characteristic that would uniquely identify the individual

Data Analysis Plan

(1) Statistical Analyses. Each participant will be assigned a unique identifier for tracking purposes and all raw data will be uploaded to the secure database in REDCap. We will explore all variables using descriptive statistics. To address the Aims 1-2, we will use a linear mixed effects model. To address Aim 3, we will apply usual mediation techniques.

Confidentiality of Specimens and Banking

Salivary specimens and cheek swabs are canceled due to Covid-19. Specimens collected prior to Covid-19 were handled as follows. Salivary specimens and cheek swabs will be collected and banked until full processing can occur. The specimens will be stored in the Frances Payne Bolton School of Nursing biomarker laboratory. Specimen testing is funded with internal monies; therefore, specimens will not be transferred to other researchers at this time.

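### Aim 2 (mediation) is given only an unspecified mixed model and the mediation methods are attached to Aim 3; unless baseline mediator and baseline outcome are both adjusted for, stable differences between teens could be reported as mediation.

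*Combined protocol and SAP*

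**What the plan says.** The statistical method is two sentences in the Data Analysis Plan, item (1) Statistical Analyses: "To address the Aims 1-2, we will use a linear mixed effects model", and then "To address Aim 3, we will apply usual mediation techniques".

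The Objectives number the aims differently. Aim 2 asks whether the effects of TRUST "are mediated by (respiratory sinus arrhythmia [RSA], behavioral interaction assessment, adolescent/parent trust self-reports, relationship quality, self-regulation" and several further variables. Aim 3 is to "Assess the effects of potential moderators (gender, race, perceived stress, parental monitoring, household income" and others. Read literally, the mediation aim gets a mixed model and the moderation aim gets mediation techniques.

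Neither sentence names a mediator or outcome visit, a covariate, a random effect, an estimator of the indirect effect or the role of baseline values. The plan does not say that baseline is included, and it does not say that it is left out.

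The table headed "Study Variables, Measures, and Data Collection Points" schedules every Aim 1 outcome, and every survey mediator with a listed instrument, at baseline, 3 months and 6 months. RSA and the behavioral interaction are scheduled at baseline and 3 months only, and both are paused. I find no instrument in the table for two Aim 2 mediators, social support and decision making.

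The Background, item (2), reports that "low interpersonal trust is associated with risky health behaviors⁵ and high depressive symptoms in low income adolescents". It gives no size for that association.

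**The concern.** An indirect effect is the product of two paths. Arm to mediator is a randomised comparison. Mediator to outcome is observational, even inside a trial. A teen who is persistently low on trust and high on symptoms contributes to a mediator-outcome slope whether or not raising trust does anything for symptoms. If TRUST then moves the mediator, that slope is multiplied by a real shift and appears as an indirect effect.

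Ordering the visits does not cure this, because a stable trait is present at every visit. Using the baseline visit as one more repeated measure in a random-intercept model does not cure it either. So the gap goes beyond missing detail: an ordinary fit of the named method would be biased.

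At stake is the mechanism claim of the study, that building trust is what improves symptoms. The randomised comparison in Aim 1 is not affected.

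**Working it through.** The plan has no figure to reproduce for this point.

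**Inputs from the documents.** 30 dyads (Number of Research Participants). Blocks of 10 with groups of 5, from which I infer 15 per arm. Visits at baseline, 3 and 6 months.

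**Assumed inputs.** Mediator M and outcome Y have unit variance and share only a stable trait. Reliability, which here equals visit-to-visit stability, is s = 0.7. The trait correlation is -0.5 or -0.7, so the observed correlation is r = 0.7 × (-0.5) = -0.35 or 0.7 × (-0.7) = -0.49. TRUST shifts the 3-month mediator by a = 0.5 SD. The true effect of M on Y is zero. Tests are two-sided at 0.05.

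**Large-sample mediator coefficient b, 6-month Y on 3-month M and arm.**

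1. No baseline terms: b = r.
2. Baseline M added: b = r(1 − s)/(1 − s²) = r/(1 + s) = r/1.7. Splitting M into baseline and change gives the same b, because it only re-expresses this model.
3. Baseline M and baseline Y added: M3 and M0 share one coefficient b, and Y0 has coefficient c. Solve b(1 + s) + c·r = r and 2b·r + c = s. This gives b = r(1 − s)/(1 + s − 2r²).
   - r = -0.35: -0.35 × 0.3 / (1.7 − 0.245) = -0.105/1.455 = -0.072.
   - r = -0.49: -0.49 × 0.3 / (1.7 − 0.4802) = -0.147/1.2198 = -0.121.

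**Spurious indirect effect, a × b, in SD.**

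| Model | r = -0.35 | r = -0.49 |
|---|---|---|
| No baselines | 0.5 × -0.35 = -0.175 | 0.5 × -0.49 = -0.245 |
| Baseline M only, or baseline/change split | 0.5 × -0.206 = -0.103 | 0.5 × -0.288 = -0.144 |
| Baseline M and baseline Y | 0.5 × -0.072 = -0.036 | 0.5 × -0.121 = -0.060 |

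Baseline M alone leaves 1/1.7 = 59% of the bias. Both baselines leave 0.036/0.175 = 21% and 0.060/0.245 = 24%.

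**Random-intercept mixed model with M entered as measured (simulated, same assumptions).** The spurious b is about -0.15 to -0.28 with all three visits and -0.22 to -0.38 with post-baseline visits only. Multiplied by 0.5, that is about -0.08 to -0.14 SD and -0.11 to -0.19 SD. When M is split into within-person and between-person parts, the within-person b is about zero.

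**False positives at 30 dyads (simulated, a = 0.5 SD).**

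| | No baselines | Both baselines |
|---|---|---|
| Mediator-outcome path significant | about 47% to 79% | about 6.5% to 10% |
| Both paths significant | about 11% to 20% | 3% to 4% |

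**Wider assumptions.** I let the size of r run from 0.3 to 0.5 and s from 0.5 to 0.7. Both paths are then falsely significant, without and with baselines, in:

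- a = 0: 2% to 4% against at most 1%
- a = 0.5 SD: 8% to 22% against 2% to 7%
- a = 0.8 SD: 19% to 44% against 5% to 16%

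Over this range the large-sample b is 0.30 to 0.50 in size without baselines, 0.18 to 0.33 with baseline M and 0.06 to 0.25 with both. At s = 0.5 and r = 0.5, both baselines still leave 0.249/0.499 = 50% of the bias.

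**The case against.** The strongest reply is that the plan is silent rather than wrong. A mixed model over three visits may use baseline, and with the labels crossed the mixed-model sentence may not be meant as the mediation analysis at all. That stands as far as it goes: the documents do not support saying that the plan excludes baseline. But silence leaves the default fit, and the default fit stays biased even with baseline as a repeated visit.

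Four stronger readings are tempting and are not supported.

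- **That the trial will report a false indirect effect.** This requires TRUST to shift the mediator. With no shift, the mean indirect effect is about zero and both paths are significant in only 2% to 4% of trials.
- **That 47% to 79% is the rate of false mediation.** Those figures are for the mediator-outcome path alone. The rate for both paths is about 11% to 20%.
- **That the preliminary data prove confounding for parent trust.** By title, the two works cited concern trust of healthcare providers, and no effect size is given. They make a stable association plausible and no more.
- **That the trial's main result is undermined.** Aim 1 is a randomised comparison, and the design is labelled an exploratory pilot.

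Perfectly stable traits are also an unfavourable assumption, and the figures should be read in that light.

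**Conclusion.** The concern holds in this form. The Aim 2 mediation model is not specified, the methods for Aims 2 and 3 are attached to the wrong aims, and the method named for Aim 2 could turn stable differences between teens into apparent mediation if TRUST moves the mediator.

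Under the main assumptions, adjusting for both baselines removes 76% to 79% of the spurious indirect effect and cuts the rate of two falsely significant paths from about 11%–20% to 3%–4%. The gain is smaller if the measures are less stable. Every size here rests on assumed correlations, reliability and shift, because the documents give none. The direction needs only some stable association between mediator and outcome. For an exploratory pilot this should be corrected, but it does not threaten the randomised comparison.

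**What to change.** In the Data Analysis Plan:

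1. Correct the labels so that mediation methods belong to Aim 2, and name a moderation method for Aim 3.
2. State that Aim 2 uses the 3-month mediator and the 6-month outcome, with **both** the baseline mediator and the baseline outcome in the mediator equation and in the outcome equation. Baseline mediator alone, or a baseline/change split alone, is not equivalent and leaves more than half the bias.
3. As an acceptable alternative, use a mixed model that separates the within-person from the between-person part of the mediator, and take the indirect effect from the within-person part only.
4. Label all indirect effects exploratory. Measurement error in the baseline values leaves some bias.

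The cost is a few sentences of text and about two degrees of freedom. No new data are needed for the survey mediators with a listed instrument. RSA and the behavioral interaction can be handled this way only where both their baseline and 3-month assessments were done.
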